15.6 Sample Size

This is intended to be small phase 1 study of an orphan disease focusing on safety and tolerability as primary endpoints. We anticipate recruiting up to 18 patients for studying an orphan disease, taking into account recruitment feasibility and the 3+3 dose escalation paradigm with an MTD cohort expansion.

16 DATA COLLECTION, RETENTION AND CLINICAL MONITORING

16.1 Data Collection Instruments

The Investigator will prepare and maintain adequate and accurate source documents designed to record all observations and other pertinent data for each participant who signs informed consent.

Study personnel at Seattle Children's will enter data from source documents corresponding to a participant's visit into the protocol-specific electronic CRF when the information corresponding to that visit is available. This will be done according to the study timeline detailed in the protocol. The epilepsy diary, in particular, will be submitted directly by the parents on a daily basis electronically through REDCap to reduce memory bias. Participants will not be identified by name in the study database or on any study documents to be collected by the Sponsor (or designee), but will be identified by a site number, participant number and initials.

If a correction is required for a CRF, the time and date stamp tracks the person entering or updating CRF data and create an electronic audit trail.

The Investigator is responsible for all information collected on participants enrolled in this study. All data collected during the course of this study must be reviewed and verified for completeness and accuracy by the Investigator. At the completion of the study, a copy of the CRF data will be archived and retained by the site Investigator.

Data Management Procedures

SCH utilizes REDCap for their EDC studies. The REDCap EDC system is designed to be US Code of Federal Regulations (CFR) 21 Part 11 compliant, with a robust audit trail system and electronic signature capabilities. Study personnel will enter data from a participant's visit onto electronic CRF screens via a web browser. Study participants will not be identified by name in the study database or on any data capture screens but will be identified by initials and a unique participant identification number. The Biostatistics and Clinical Data Management group will be responsible for data processing, in accordance with procedural documentation. Database lock will occur once quality assurance procedures have been completed. All procedures for the handling and analysis of data will be conducted using good computing practices for the handling and analysis of data for clinical trials.

Data Quality Control and Reporting

After data have been entered into the study database, data validation checks will be applied on a regular basis. Queries are entered, tracked, and resolved through the EDC system directly. The study database will be updated in accordance with the resolved queries. All changes to the study database will be documented in an audit trail.

Security and Archival of Data

The EDC system is hosted by REDCap. Data are regularly backed up.

REDCap maintains 21 CFR Part 11-compliant electronic systems, with procedures in place to safeguard against unauthorized acquisition of data. Any authorized communication with the REDCap is conducted via SSL (128-bit) encryption. Robust password procedures, consistent with 21 Part 11, are in place. Robust physical security procedures are in place at the Data Center to prevent unauthorized personnel physical access to the server rooms. EDC account access is maintained and monitored by the Biostatistics and Clinical Data Management.

Other databases will be stored on Seattle Children's servers and are safeguarded against unauthorized access by established security procedures. Network accounts are password protected and maintained and monitored by Seattle Children's. Data is backed up regularly according to the Information Services group's procedures.

16.2 Availability and Retention of Investigational Records

The Investigator must make study data accessible to the monitor, other authorized representatives of the Sponsor (or designee), IRB, or Regulatory Agency (e.g., FDA) inspectors upon request. A file for each participant must be maintained that includes the signed Informed Consent, HIPAA Authorization, Assent Form (if applicable) and copies of all source documentation related to that participant. The Investigator must ensure the reliability and availability of source documents from which the information on the CRF was derived.

All study documents (e.g., participant files, signed informed consent forms, copies of CRFs, Essential Document and Study Reference Binders) must be kept secured for a period of two years following marketing of the investigational product or for two years after centers have been notified that the IND has been discontinued or for a non-IND study for five years after database lock. There may be other circumstances for which the Sponsor is required to maintain study records and, therefore, the Sponsor should be contacted prior to removing study records for any reason.

16.3 Monitoring

By signing this protocol, the Investigator grants permission to the appropriate regulatory authorities to conduct on-site monitoring and/or auditing of all appropriate study documentation. Monitoring visits will be conducted according to the U.S. CFR 21 Part 312 and ICH Guidelines for GCP (E6) and to ensure investigator compliance to 21 CFR Parts 50, 56 and 312 and to GCP.

16.4 Participant Confidentiality

In order to maintain participant confidentiality, only a site number, participant number and participant initials will identify all study participants on CRFs and other documentation. Additional participant confidentiality issues (if applicable) are covered in the Clinical Study Agreement.

17 ADMINISTRATIVE, ETHICAL, REGULATORY CONSIDERATIONS

The study will be conducted according to the Declaration of Helsinki, Protection of Human Volunteers (21 CFR 50), Institutional Review Boards (21 CFR 56), and Obligations of Clinical Investigators (21 CFR 312).

To maintain confidentiality, all laboratory specimens, evaluation forms, reports and other records will be identified by a coded number and initials only. Clinical information will not be released without written permission of the participant, except as necessary for monitoring by the FDA. The Investigator must also comply with all applicable privacy regulations (e.g., Health Insurance Portability and Accountability Act of 1996, EU Data Protection Directive 95/46/EC).

17.1 Protocol Amendments

Protocol amendments cannot be implemented without prior written IRB approval except as necessary to eliminate immediate safety hazards to participants. A protocol amendment intended to eliminate an apparent immediate hazard to participants may be implemented immediately, provided the IRBs are notified within five working days.

17.2 Institutional Review Board

The protocol and consent form will be reviewed and approved by the IRB prior to study initiation. Serious adverse experiences regardless of causality will be reported to the IRB in accordance with the standard operating procedures and policies of the IRB, and the Investigator will keep the IRB informed as to the progress of the study. The Investigator will obtain assurance of IRB compliance with regulations.

Any documents that the IRB may need to fulfill its responsibilities (such as protocol, protocol amendments, Investigator's Brochure, consent forms, information concerning participant

recruitment, payment or compensation procedures, or other pertinent information) will be submitted to the IRB. The IRB's written unconditional approval of the study protocol and the informed consent form will be in the possession of the Investigator before the study is initiated. The IRB's unconditional approval statement will be transmitted by the Investigator to AADi prior to the shipment of study supplies to the site. This approval must refer to the study by exact protocol title and number and should identify the documents reviewed and the date of review.

Protocol and/or informed consent modifications or changes may not be initiated without prior written IRB approval except when necessary to eliminate immediate hazards to the participants or when the change(s) involves only logistical or administrative aspects of the study. Such modifications will be submitted to the IRB and written verification that the modification was submitted and subsequently approved should be obtained.

The IRB must be informed of revisions to other documents originally submitted for review, serious and/or unexpected adverse experiences occurring during the study in accordance with the standard operating procedures and policies of the IRB, new information that may affect adversely the safety of the participants of the conduct of the study, an annual update and/or request for re-approval, and when the study has been completed.

17.3 Informed Consent Form

Informed consent will be obtained in accordance with the Declaration of Helsinki, ICH GCP, US Code of Federal Regulations for Protection of Human Subjects (21 CFR 50.25[a,b], CFR 50.27, and CFR Part 56, Subpart A), the Health Insurance Portability and Accountability Act (HIPAA, if applicable), and local regulations.

The Investigator will prepare the informed consent form, assent and HIPAA authorization and provide the documents to the Sponsor or designee for approval prior to submission to the IRB. The consent form generated by the Investigator must be acceptable to the Sponsor and be approved by the IRB. The written consent document will embody the elements of informed consent as described in the International Conference on Harmonisation and will also comply with local regulations. The Investigator will send an IRB-approved copy of the Informed Consent Form to the Sponsor (or designee) for the study file.

A properly executed, written, informed consent will be obtained from each participant prior to entering the participant into the trial. Information should be given in both oral and written form and participants (or their legal representatives) must be given ample opportunity to inquire about details of the study. If appropriate and required by the local IRB, assent from the participant will also be obtained. If a participant is unable to sign the informed consent form (ICF) and the HIPAA authorization, a legal representative may sign for the participant. A copy of the signed consent form (and assent) will be given to the participant or legal representative of the participant and the original will be maintained with the participant's records.

During the course of the study, if modifications are made to the consent form that impact the participant, the participant will be re-consented as described above.

17.4 Publications

The preparation and submittal for publication of manuscripts containing the study results shall be in accordance with a process determined by mutual written agreement among the study Sponsor and participating institutions. The publication or presentation of any study results shall comply

with all applicable privacy laws, including, but not limited to, the Health Insurance Portability and Accountability Act of 1996.

17.5 Investigator Responsibilities

By signing the Agreement of Investigator form, the Investigator agrees to:

1. Conduct the study in accordance with the protocol and only make changes after notifying the Sponsor (or designee), except when to protect the safety, rights or welfare of subjects.
2. Personally conduct or supervise the study (or investigation).
3. Ensure that the requirements relating to obtaining informed consent and IRB review and approval meet federal guidelines, as stated in § 21 CFR, parts 50 and 56.
4. Report to the Sponsor or designee any AEs that occur in the course of the study, in accordance with §21 CFR 312.64.
5. Ensure that all associates, colleagues and employees assisting in the conduct of the study are informed about their obligations in meeting the above commitments.
6. Maintain adequate and accurate records in accordance with §21 CFR 312.62 and to make those records available for inspection with the Sponsor (or designee).
7. Ensure that an IRB that complies with the requirements of §21 CFR part 56 will be responsible for initial and continuing review and approval of the clinical study.
8. Promptly report to the IRB and the Sponsor (or designee) all changes in the research activity and all unanticipated problems involving risks to subjects or others (to include amendments and IND safety reports).
9. Seek IRB approval before any changes are made in the research study, except when necessary to eliminate hazards to the participants/subjects.
10. Comply with all other requirements regarding the obligations of clinical investigators and all other pertinent requirements listed in § 21 CFR part 312.

APPENDIX 1. SCHEDULE OF EVENTS

	SCREENING DAY -14 TO DAY 0*	VISIT 1: DAY 0	VISIT 2: DAY 30**	VISIT 3: DOSE 1	VISITS 4&5: DOSES 2 AND 3	VISIT 6: ONE WEEK POST- DOSING	VISITS 7&8: 30 AND 60 DAYS POST-DOSING	VISIT 9: 90 DAYS POST- DOSING	EARLY PERMANENT DISCONTINUATION
Informed Consent Process	X								
Enrollment Eligibility Checklist	X								
Demographics	X								
Extended Physical Exam	X								
Neurological Exam	X								
Hepatitis C, and Hepatitis B, HIV if necessary ^A	X								
Epilepsy and Medical History	X								
Height, Weight, and BSA	X			X				X	X
Vitals	X		X	X	X	X			
Pulse Oximetry ^F	X		X	X	X				
CBC with Differential ^C	X		X	X	X	X	X ^B (visit 7 only)		X
Serum Chemistries with Coagulation Assessment ^E	X		X	X	X ^B (visit 4 required)	X ^B	X ^B (visit 7 only)		X
Urine Pregnancy ^G	X		X						
Study Continuation Checklist			X	X	X	X	X		
Abbreviated Physical Exam		X	X	X	X	X	X ^D		X
Concomitant Medication Review		X	X	X	X	X	X	X	X
Dispense Seizure Diary and Glossary		X							
Administer QOLCE, NCBRF, & C-SSRS			X			X		X	X
Review Seizure Diary			X	X	X	X	X		X
Investigator Opinion			X	X	X	X	X		
Dosing Checklist				X	X				
Study Drug Administration				X	X				
Adverse Events			X	X	X	X	X	X	X
Whole Blood Rapamycin Level ^H					X	X			X

*Screening may be combined with Visit 1

**Visit 2 may also be Visit 3 Dose 1

^A Hepatitis C (and if necessary, Hepatitis B) test: 2 mL SST gold top tube. HIV seropositivity test, if necessary: 2 mL gold top tube. If testing for all together, can use one 4 mL SST gold top tube.

^B Only if previous chemistries or coagulation profiles are abnormal or are otherwise clinically indicated.

^C CBC with differential: 1 mL EDTA lavender top tubes if testing with blood trough rapamycin levels. If testing alone can collect only 0.5 mL in EDTA tube.

^D Only at 30 days post-treatment

^E 2 x 4 mL SST gold top tubes. Serum chemistry: Na, K, Cl, CO₂, Ca, fasting glucose, BUN, creatinine, total protein, albumin, total bilirubin, aspartate aminotransferase (AST/SGOT), alanine aminotransferase (ALT/SGPT), alkaline phosphatase, uric acid, Ph, fasting serum lipid profile. Coagulation assessment: 1.8 mL Sodium Citrate light blue top tubes. Coagulation assessment including prothrombin time, partial thromboplastin time, international normalized ratio (PT/PTT/INR).

^F Must be greater than 93% on room air to continue with study procedures

^G Only participants of child-bearing potential, and only monthly at most. If serum test is needed to confirm positive urine test, 1 mL SST gold top tube

^H 0.5 mL EDTA lavender top tube if testing alone. Refrigerate if drawing on a Friday or when there may be a delay in lab processing.

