8.7.4 Management of non-infectious pneumonitis

Non-infectious pneumonitis is a class effect of rapamycin derivatives. Cases of non-infectious pneumonitis (including interstitial lung disease) have also been described in participants taking mTOR inhibitors. Some of these have been severe and on rare occasions, a fatal outcome was observed.

A diagnosis of non-infectious pneumonitis should be considered in participants presenting with nonspecific respiratory signs and symptoms such as hypoxia, pleural effusion, cough or dyspnea, and in whom infectious, neoplastic and other non-medicinal causes have been excluded by means of appropriate investigations. Participants should be advised to report promptly any new or worsening respiratory symptoms. Participants who develop radiological changes suggestive of non-infectious pneumonitis and have few or no symptoms may continue mTOR inhibitor dosing without dose alteration. If symptoms are moderate (Grade 2), consideration should be given to interruption of dosing until symptoms improve. The use of corticosteroids may be indicated. mTOR inhibitor may be reintroduced once at a reduced dose until recovery to Grade 1 or better. For cases where symptoms of non-infectious pneumonitis are severe (Grade 3), mTOR inhibitor dosing should be discontinued and the use of corticosteroids may be indicated until clinical symptoms resolve. Dosing with mTOR inhibitors may be re-initiated at a reduced dose depending on individual clinical circumstances.

Table 5. Pneumonitis Management and ABI-009 Dosing

Pneumonitis Grade	Required Investigations	Management of Pneumonitis	ABI-009 Dose Adjustment
Grade 1	CT scans with lung windows and pulmonary function testing including spirometry, DLCO, and room air O ₂ saturation at rest. Repeat chest x-ray/CT scan every 2 cycles until return to baseline.	No specific therapy required.	Administer 100% of ABI-009 dose
Grade 2	CT scans with lung windows and pulmonary function testing including spirometry, DLCO, and room air O ₂ saturation at rest. Repeat chest x-ray/CT scan every cycle until return to baseline. Consider bronchoscopy.	Symptomatic therapy. If cough is troublesome prescribe corticosteroids.	Reduce ABI-009 dose until recovery to \leq Grade 1. ABI-009 may also be interrupted if symptoms are troublesome. Participants will be withdrawn from the study if they fail to recover to \leq Grade 1 within 3 weeks.

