9.1.7 Vital Signs

Resting (preferably a minimum of 5 minutes) measurements of body temperature, blood pressure, pulse and respirations will be performed and recorded as noted in the Schedule of Events.

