9.1.8 Oximetry

A resting (preferably a minimum of 5 minutes) measurement of oximetry will be measured on room air and recorded at as noted in the Schedule of Events.

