10.4 Visits 3, 4, & 5: ABI-009 Doses 1-3 (+/-2 days)

1. Review adverse events.
2. Review epilepsy diary.
3. Investigator opinion regarding seizures recorded: same, worse, somewhat better, better.
4. Record changes to concomitant medications.
5. Perform abbreviated physical exam
6. Measure and record height and weight.
 - a. BSA calculation (Calculated ONLY on Dose 1 visit; to be recalculated only if the weight changes by > 10% in subsequent cycles)
7. Obtain and record vital signs. Pulse oximetry must be >93 to continue.
8. Collect blood for clinical laboratory tests (chemistry, hematology).
9. Laboratory assessments as required per the schedule of evaluations
 - a. Complete Blood Count (CBC) with differential and platelet count
 - b. Blood chemistry assessment (required for Visit 4), including:
 - i. Sodium, potassium, chloride, bicarbonate, calcium, fasting glucose, albumin,
 - ii. Total protein, BUN, serum creatinine.
 - iii. Total bilirubin, AST, ALT, alkaline phosphatase, uric acid, phosphorus,
 - iv. Fasting serum lipid profile (total cholesterol, triglycerides, HDL and LDL)
10. Coagulation assessment, including prothrombin time, partial thromboplastin time, international normalized ratio (PT/PTT/INR)
11. Whole blood rapamycin trough levels
12. Dose modification as appropriate (only in the case of toxicities mandating a dose change as per section 8.6)
13. Administer study drug

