10.5 Visit 6: Post-Dosing One-Week Assessment (+/-2 days)

1. Review adverse events.
2. Review epilepsy diary.

3. Investigator opinion regarding seizures recorded: same, worse, somewhat better, better.
4. Record changes to concomitant medications.
5. Perform abbreviated physical examination.
6. Obtain and record vital signs.
7. Collect urine for pregnancy test (if child-bearing potential).
 - a. If positive confirm with blood test
8. Collect blood for clinical laboratory tests (chemistry, hematology).
9. Laboratory assessments as required per the schedule of evaluations
 - c. Complete Blood Count (CBC) with differential and platelet count
 - d. Blood chemistry assessment, including:
 - i. Sodium, potassium, chloride, bicarbonate, calcium, fasting glucose, albumin,
 - ii. Total protein, BUN, serum creatinine.
 - iii. Total bilirubin, AST, ALT, alkaline phosphatase, uric acid, phosphorus,
 - iv. Fasting serum lipid profile (total cholesterol, triglycerides, HDL and LDL)
10. Coagulation assessment, including prothrombin time, partial thromboplastin time, international normalized ratio (PT/PTT/INR)
11. Whole blood rapamycin trough level
12. Administer C-SSRS, QOLCE, and NCBRF

10.6 Follow-up Visits 7, 8, & 9: 30, 60, and 90 Days Post-Dosing (+/-7 days)

1. Review participant diary for compliance and seizure frequency.
2. Safety follow-up labs at Visit 7 per PI discretion following Visit 6 labs.
3. Investigator opinion regarding seizures recorded: same, worse, somewhat better, better
4. Record changes to concomitant medications.
5. Perform abbreviated physical exam (30 days post-doing only).
6. Measure and record height and weight (at final study visit).
7. Obtain and record vital signs (30 days post-dosing only).
8. On final visit (90 days post-dosing) administer C-SSRS, QOLCE and NCBRF

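### No pulse oximetry reading is scheduled after the third dose or at the early discontinuation visit, which leaves a gap in routine detection of low-symptom desaturation

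*Combined protocol and SAP*

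**What the plan says.** Section 9.1.8 makes oximetry a procedure of its own and leaves its timing to Appendix 1: "measurement of oximetry will be measured on room air and recorded at as noted in the Schedule of Events". The Appendix 1 row "Pulse Oximetry ^F" is marked at screening, Visit 2, Visit 3 and Visits 4 and 5. It is blank at Visit 1, Visit 6, Visits 7 and 8, Visit 9 and early permanent discontinuation. Footnote F gives the purpose: "Must be greater than 93% on room air to continue with study procedures".

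The visit lists agree with the table. Sections 10.1, 10.3 and 10.4 name oximetry; for the dosing visits 10.4 says "Pulse oximetry must be >93 to continue". Section 10.5 (Visit 6) says only "Obtain and record vital signs", and 10.6 and 10.7 likewise list vital signs without oximetry. Section 9.1.7 defines vital signs as "measurements of body temperature, blood pressure, pulse and respirations", so saturation is not part of them.

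Section 8.7.4 describes non-infectious pneumonitis as a class effect that is sometimes severe and rarely fatal. It says the diagnosis should be considered in participants with "nonspecific respiratory signs and symptoms such as hypoxia, pleural effusion, cough or dyspnea".

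**The concern.** Safety, including DLT and MTD, is the primary endpoint (3.1 and 5.1). The protocol names hypoxia as one prompt for considering a serious class toxicity, yet it measures saturation only while a dosing decision is pending. Once the last infusion is given, the scheduled measurement stops.

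Appendix 1 schedules no chest imaging or lung function testing, so oximetry is the only scheduled measurement of oxygenation. Section 8.7.4 itself allows for pneumonitis with few or no symptoms. Symptom reporting may also be limited here: participants may be as young as 3 years (6.2), and 1.1 describes frequent intellectual impairment in uncontrolled childhood epilepsy. At stake is whether a fall in saturation after Dose 3 that causes little complaint would be noticed and recorded.

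**Working it through.** The plan states no figure on this point. The check sets the schedule against the visit lists and then counts days.

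**Inputs.** Three doses seven days apart (4.1), with intervals of 5 to 9 days allowed (8.4.1); Visit 6 one week after dosing (10.5); Visits 7, 8 and 9 at 30, 60 and 90 days after dosing (10.6); a DLT window of 30 days from dosing (8.5). Assumptions: Dose 1 is Day 0, and follow-up visits are counted from Dose 3.

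**Step 1: table against text.**

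| Visit | Nominal day | Oximetry in Appendix 1 | Oximetry in Section 10 |
|---|---|---|---|
| Screening | before Dose 1 | yes | yes (10.1) |
| Visit 1 | before Dose 1 | no | no (10.2) |
| Visit 2 | before Dose 1 | yes | yes (10.3) |
| Visits 3, 4, 5 | 0, 7, 14 | yes | yes (10.4) |
| Visit 6 | 14 + 7 = 21 | no | no (10.5) |
| Visits 7, 8, 9 | 14 + 30 = 44, 14 + 60 = 74, 14 + 90 = 104 | no | no (10.6) |
| Early discontinuation | variable | no | no (10.7) |

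Table and text agree at every visit, so the blank cells are not an artefact of reading the PDF.

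**Step 2: order within a dosing visit.** In 10.4 oximetry is item 7 and drug administration is item 13, and the reading is a condition for continuing. Each reading therefore precedes that day's infusion. Scheduled readings following Dose 1: 2 (before Doses 2 and 3). Following Dose 2: 1. Following Dose 3: 0.

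**Step 3: time after the last scheduled reading.**
- DLT window counted from the last dose: it ends on Day 14 + 30 = 44. Days from Dose 1 with no further scheduled reading: 30/44 = 68%. With 5 to 9 day intervals Dose 3 falls on Day 10 to 18, giving 30/40 = 75% to 30/48 = 63%.
- DLT window counted from Dose 1, since 8.5 does not say which dose starts it: it ends on Day 30. Days after Dose 3: (30 − 14)/30 = 53%, with a range of 20/30 = 67% to 12/30 = 40%.

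**Step 4: visits that could carry a reading.** Visit 6 falls 7 ± 2, that is 5 to 9, days after Dose 3, inside a window counted from that dose. Visit 7 falls 30 ± 7, that is 23 to 37, days after Dose 3, so it may lie inside or outside. Examination and vital signs are already listed at both visits and at early discontinuation (10.5 to 10.7).

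**Step 5: a related mismatch.** Sections 10.6 and 10.7 list vital signs at Visit 7 and at early discontinuation. The Vitals row of Appendix 1 is blank at both.

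**The case against.** The strongest reply is that oximetry here is a gate for dosing. After Dose 3 nothing remains to be gated, so ending it is consistent, and no section promises a later reading. Other surveillance also continues. The abbreviated examination includes a respiratory assessment, and new abnormal findings must be recorded as adverse events (9.1.5). It is done at Visit 6, Visit 7 and early discontinuation. Adverse events are asked about at each visit (11.1), the daily diary records new symptoms (9.1.11), and participants are told to report respiratory symptoms promptly (8.7.4). All of this stands. It narrows the gap but does not close it, because none of these measures saturation.

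Three stronger readings are tempting, and the documents do not support them.

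- A reader might infer that saturation is never measured after Dose 3, even in a participant who stops for suspected lung toxicity. Table 5 requires resting room-air saturation at every pneumonitis grade. Section 11.4 requires at least weekly follow-up after discontinuation for a suspected drug-related event. Section 12.1 asks early stoppers to complete their remaining visits, which may include Visits 4 or 5. What is missing is the routine reading. The Table 5 measurement cannot fully replace it, since hypoxia is one of the signs that would start that work-up.
- A reader might infer that DLTs will be missed and escalation distorted. A DLT needs grade 3 or higher and probable or definite attribution (8.5). Section 8.7.4 ties grade 3 pneumonitis to severe symptoms, and the fallback scale in Table 7 puts asymptomatic findings at grade 1. The protocol does not reproduce the CTCAE grading of hypoxia, so an effect on the DLT count can be neither shown nor excluded from the documents.
- A reader might treat the 14 of 104 days up to the last reading as 13% coverage, or argue that monitoring stops just as cumulative toxicity peaks. Spot readings do not cover days, and 2.1 describes the class's adverse events as non-cumulative.

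**Conclusion.** The point holds as a gap in scheduled, routine ascertainment. No saturation reading is scheduled at any of the four visits after Dose 3 or at the early discontinuation visit. If the DLT window runs from the last dose, its final 30 days contain none; if it runs from Dose 1, the nominal figure is 16 of 30 days. These counts describe time after the last scheduled reading and do not estimate the number of missed events, for which the documents give no basis.

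The likely consequence is an incomplete adverse event record for low-symptom desaturation. An effect on the DLT count is possible: in cohorts of three, one DLT is enough to require three more participants (4.1). That effect is not demonstrated. The change is worth making because safety is primary and the reading is already in use in this trial, but the gap does not undermine the dose-finding design.

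The conclusion rests on the Section 10 lists and Appendix 1 being complete, and on vital signs meaning what 9.1.7 says.

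**What to change.** 1. Add the resting room-air reading of 9.1.8 at Visit 6, Visit 7 and the early discontinuation visit, in Appendix 1 and in 10.5, 10.6 and 10.7. Visit 6 is the most useful, as it falls early after Dose 3.
2. Include saturation values, and their change from baseline, in the 15.3 safety summaries, which do not mention them now.
3. In the same edit, reconcile the Vitals row of Appendix 1 with 10.6 and 10.7 at Visit 7 and early discontinuation.

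The cost is a non-invasive reading of a few minutes at visits already attended, plus schedule wording. The downside is a few more incidental low readings to follow up. No dose, threshold or stopping rule changes. If the sponsor prefers not to add the readings, the protocol should say that saturation after Dose 3 is measured for cause only, so that the safety tables are read accordingly.
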